### 5.2 EXCLUSION CRITERIA

An individual who meets any of the following criteria will be excluded from participation in this study:

- Desire another pregnancy in less than 6 months
- Do not intend to exclusively breastfeed
- Do not have access to a telephone
- Have any medical contraindication to POPs
- Have any contraindication to breastfeeding, including maternal illegal drug use, history of breast augmentation or reduction, infant with major congenital anomaly
- Cognitively impaired
- Currently incarcerated

### 5.3 SCREEN FAILURES

For individuals who do not meet the criteria for participation in this trial (screen failure) due to not meeting eligibility requirements, the reason will be documented. Potential participants who decline

participation will be noted and counted as well. No identifying information will be collected from screen failures.

## 6 STUDY INTERVENTION

### 6.1 STUDY INTERVENTION

Group 1: Initiation of d-POPs 120-160 hours after delivery (N=10)

Group 2: Initiation of n-POPs 120-160 hours after delivery (N=10)

Group 3: Initiation of d-POPs 4 weeks after delivery (N=10) [placebo starting 120-160 hours, continuing for 28 days]

### 6.2 MEASURES TO MINIMIZE BIAS: RANDOMIZATION AND BLINDING

Participants will be randomized to their assigned group by chance with a computer-generated randomization scheme. The participant and investigator will both be blinded to the group assignment. The investigational pharmacy will be aware of the group assignment of each participant and will encapsulate and prepare the blinded medications for the research coordinator to deliver to the participant.

## 7 STUDY INTERVENTION DISCONTINUATION AND PARTICIPANT DISCONTINUATION/WITHDRAWAL

### 7.1 DISCONTINUATION OF STUDY INTERVENTION

If a participant chooses not to move forward with initiation of the study POPs, she will remain in the study under observation. Remaining study procedures should be completed as indicated by the study protocol. Reasons for choosing another method of contraception will be documented and the participant followed for the study duration of 8 weeks.

### 7.2 PARTICIPANT DISCONTINUATION/WITHDRAWAL FROM THE STUDY

Participants may withdraw voluntarily from the study at any time. The PI or study team will not withdraw anyone from the study without specific request from the participant. Medical care will be provided by the patient's clinician as standard of care in the case of study withdrawal. Research participants who sign the informed consent form, and are randomized and receive the study intervention, and subsequently withdraw, or are withdrawn or discontinued from the study will not be replaced.

### 7.3 LOST TO FOLLOW-UP

A participant will be considered lost to follow-up if she fails to return for any scheduled visits and is unable to be contacted by the study site staff.

The following actions must be taken if a participant fails to respond to surveys or return to the clinic for the required study visit:

- The research coordinator will attempt to contact the participant, re-send surveys and reschedule the missed visit within one week and counsel the participant on the importance of maintaining the assigned visit schedule and ascertain if the participant wishes to and/or should continue in the study.
- Before a participant is deemed lost to follow-up, the investigator or designee will make every effort to regain contact with the participant, including 3 telephone calls or texts. These contact attempts should be documented in the participant's study file.

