Until recently, POPs containing 0.35 mg daily of the oral progestin Norethindrone (n-POPs) have been the only available POP (Table 1). Norethindrone is a variant of progestin derived from testosterone. N-POPs do not consistently inhibit ovulation; the contraceptive mechanism of action is primarily through progestin effects on the cervical mucous and endometrium. They require daily use with a narrow window of time for intake to maintain efficacy and are associated with unpredictable vaginal bleeding patterns and acne. Fewer than half of women who intend to use n-POPs PP use the method at 3 months. Women who choose n-POPs for PP contraception are significantly more likely to have a short IPI compared to women choosing all other reversible methods.

Drospirenone is a novel progestin derived from spironolactone (Table 1). POPs containing 4 mg of oral drospirenone (d-POPs) became available for use in the U.S. in 2019. D-POPs consistently suppress ovulation and allow for a wider missed-pill window and cyclic use with hormone-free days which offer the potential to improve ease of use and to decrease irregular bleeding. Unlike norethindrone, drospirenone has anti-androgenic properties and should not exacerbate acne and may improve it. The efficacy of d-POPs among non-breastfeeding women is similar to combined estrogen-progestin pills. However, little is known about the effect of d-POPs on breastfeeding performance or PP contraceptive use, efficacy, or side effects among PP women.

Table 1: Progestin types available as progestin-only pills for contraception in the United States

Progestin	Progestin Classification	Available in U.S.	Hormone-free days, 28-day cycle	Androgen effect	Metabolized into Ethinyl Estradiol
Norethindrone	19-nor testosterone, Estrane	1970	None	Medium-high	Small amount
Drospirenone	Spironolactone	2019	4	Antiandrogenic	None

D-POPs are promoted for use while breastfeeding despite a lack of data on the effect of d-POPs on breastfeeding or infant outcomes. The package insert states, “no effects on breastfed infants are

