#### **Randomization:**

A licensed medical provider on the clinical care team will review eligibility for the method and instruct patients on use of POPs prior to discharge from the hospital and will approve a prescription for both POPs. Participants will then be randomized to (1) early d-POPs to be initiated at 120-168 hours (5-7 days) after delivery, (2) early n-POPs to be initiated at 120-168 hours after delivery, or (3) placebo for 28 days followed by d-POPs initiated at 4 weeks (28-35 days) after delivery, at a 1:1:1 ratio (Figure 2). Study staff will then provide participants with written and verbal instructions about when to initiate the method and to take the study medications in the order dispensed. Participants, care providers, and research staff will be blinded to group assignment. Participants will be instructed on lactational

amenorrhea method (LAM), a highly effective form of contraception, and will be counseled that if they no longer meet criteria for LAM, then they may be at risk for unintended pregnancy between days 28 and 33 and should use condoms or abstain from intercourse during that time. Before day 28, the CDC Selected Practice Recommendations state that a provider can be “reasonably certain that woman is not pregnant” regardless of LAM use and after day 33 all study drugs will be effective contraception regardless of group assignment.

The research team will dispense two 28-day pill packs containing either d-POPs, n-POPs, or one placebo and one d-POPs, as determined by the randomization scheme, and labeled 1st and 2nd. For participants in group 3, the first pack will contain only placebo to facilitate delayed initiation while ensuring blinding. D-POP packs will include 24 active and 4 placebo tablets per month, and n-POP packs will include 28 active tablets, packaged in order of daily use. All d-POP, n-POP, and placebo tablets will be encapsulated by the research pharmacies to have an identical appearance.

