#### **Breastmilk collection and analysis:**

Women will attend an in-person visit at 4 weeks PP with their infant. Participants will have the option to collect a mid-feeding sample at home with all pumping materials and instructions sent to her home or collect a sterile sample at the visit using a study-provided breast pump. 10 mLs of breastmilk from the collection (either refrigerated sample brought to the visit or collected on-site) will be frozen at the site of the visit at the research site. The milk samples will be frozen at -80 degrees onsite. The lab will use liquid chromatography to assess the composition of breast milk and compare the concentrations of total fat, total protein and carbohydrates including oligosaccharides.

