## 9 STATISTICAL CONSIDERATIONS

### 9.1 STATISTICAL HYPOTHESES

Comparisons will be made between groups 1 and 2 to assess differences in outcomes by type of progestin used, and between groups 1 and 3 to assess differences in outcomes by timing of progestin initiation. The primary outcome is the proportion of women exclusively breastfeeding at 8 weeks postpartum. Differences in baseline demographic characteristics and in variables between groups will be assessed using  $\chi^2$ , Fisher exact, or t-tests as appropriate.

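### The pack calendar is inconsistent: 28 placebo capsules from day 5-7 put Group 3's first d-POP capsule on day 33-35, which the day-33 statement does not fit, and the readable text sets no latest day for the 4-week milk sample

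*Combined protocol and SAP*

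**What the plan says.** **Start of pack 1.** Section 8.1 (Randomization) gives 120-168 hours for the early arms, glossed as 5-7 days. Section 6.1 gives 120-160 hours for all three groups and, for Group 3, "placebo starting 120-160 hours, continuing for 28 days".

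**Group 3's d-POP start.** Section 8.1 describes the arm as "placebo for 28 days followed by d-POPs initiated at 4 weeks (28-35 days) after delivery".

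**Packs.** Each woman receives two 28-day packs, to be taken in sequence. Section 8.1 states: "D-POP packs will include 24 active and 4 placebo tablets per month, and n-POP packs will include 28 active tablets". Group 3's first pack is all placebo. Section 2.2 says that d-POPs "allow for a wider missed-pill window and cyclic use with hormone-free days".

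**Contraceptive cover.** Section 8.1 counsels women who no longer meet the lactational amenorrhea criteria about a possible risk of pregnancy from day 28 to day 33, and says that "after day 33 all study drugs will be effective contraception regardless of group assignment".

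**Milk sample.** Section 3 takes milk composition (Aim 2) from one 4-week sample. Section 8.1 says: "Women will attend an in-person visit at 4 weeks PP with their infant". The milk may be collected at the visit, or at home and brought refrigerated. For a missed visit, Section 7.3 has the coordinator "re-send surveys and reschedule the missed visit within one week". Section 9.1 makes one comparison between Groups 1 and 2 (progestin type) and another "between groups 1 and 3 to assess differences in outcomes by timing of progestin initiation".

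**The concern.** Group 3's d-POP start can be counted from the pack contents, and the count does not give the range stated for it. The day-33 statement and the counselling period ending on day 33 use a calendar that fits only the earliest start of pack 1. These passages tell women when they are at risk, and they define the exposure difference between Groups 1 and 3.

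The milk sample depends on the same calendar. It is meant to compare women on d-POP (Group 1) with women still on placebo (Group 3). With no stated latest day, a late enough Group 3 sample comes from a woman already taking d-POP, and the timing contrast is blurred. Each arm has 10 women with one sample each, so one such sample is a tenth of an arm.

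**Working it through.** **Inputs.** The start day is s = 5, 6 or 7, with delivery as day 0, since Section 8.1 equates 120 hours with 5 days. Pack 1 holds 24 active and 4 inactive capsules in Group 1, 28 active in Group 2 and 28 placebo in Group 3 (Section 8.1). The nominal visit is day 28. Three assumptions are made: the inactive capsules are the last four, no capsule is missed, and pack 2 follows pack 1 without a gap.

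**Formula.** Capsule c is taken on day s + c - 1.

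**1. The plan's own figure, Group 3's d-POP start on day 28-35.** The first capsule of pack 2 is c = 29, taken on day s + 28 = 33, 34 or 35. The upper end is reproduced and the lower end is not: a day-28 start after 28 placebo days would need pack 1 to begin on day 0. In hours, with 28 × 24 = 672:
- 120 + 672 = 792 h (day 33)
- 160 + 672 = 832 h (day 34.7)
- 168 + 672 = 840 h (day 35)

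**2. The day-33 statement.** On day 33 a woman takes capsule 33 - s + 1 = 29, 28 or 27. Only the day-5 starter has reached d-POP. The mismatch remains under either hour limit, because the latest d-POP start is day 34.7 or day 35.

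**3. The milk sample.** Group 1's inactive capsules (25-28) fall on days s + 24 to s + 27.

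| Start day s | Capsule on day 28 | Group 1 inactive days | Group 3 first d-POP day | Delay from day 28 to Group 1 inactive | Delay from day 28 to Group 3 d-POP |
|---|---|---|---|---|---|
| 5 | 24 | 29-32 | 33 | 1 day | 5 days |
| 6 | 23 | 30-33 | 34 | 2 days | 6 days |
| 7 | 22 | 31-34 | 35 | 3 days | 7 days |

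On day 28, Group 1 is on active d-POP and Group 3 is on placebo for every start day, as intended. Group 2 is on active capsules throughout.

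**4. Group 3 samples taken on d-POP.** If Section 7.3 allows rebooking to days 29-35, the number of those 7 days on which Group 3 is on d-POP is m = 35 - (s + 28) + 1 = 8 - s = 3, 2 or 1. The documents give no late-visit rate. Assume that a proportion p of visits is late, with each of the 7 days equally likely and the sample taken on the visit day. The expected number among 10 women is 10 × p × m/7:
- p = 0.10: 10 × 0.10 × 1/7 = 0.14 to 10 × 0.10 × 3/7 = 0.43
- p = 0.30: 10 × 0.30 × 1/7 = 0.43 to 10 × 0.30 × 3/7 = 1.29

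The range is about 0.1 to 1.3 samples, from women who have reached only their first to third d-POP capsule.

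**5. Day numbering.** If delivery is counted as day 1, pack events move one day later and Group 3's first d-POP capsule falls on day 34, 35 or 36. All three start days are then still on placebo on day 33, and only the two earlier ones can reach d-POP by day 35.

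**The case against.** - **A window may exist in Figure 2.** The figure is not shown, so this stands, and the milk point is limited to the readable text. The conflicts within Section 8.1 and with Section 6.1 are in the text itself.
- **Section 7.3 is a retention rule, and its one week may limit the contact attempt rather than the visit.** This stands as a possible reading. The count in step 4 would then not apply, but the sample would have no latest day at all.
- **Days 33-35 lie inside the stated 28-35.** This stands. The range is loose at its lower end; the count does not fall outside it. A reader might infer that on-time samples can coincide with Group 3's d-POP start. That follows only if day 28 is taken literally, and the 28-capsule placebo pack does not allow it.
- **Group 1's inactive days belong to the regimen.** This stands. A reader might add late Group 1 samples (4 of the 7 days) to the count, which would more than double it, and call them contamination. Section 2.2 presents the hormone-free days as part of cyclic d-POP use, so they are left out.
- **No consequence is shown.** The endpoint is fat, protein and carbohydrate content, not drug concentration. The pilot is sized for feasibility (Section 9.2), and milk composition is not the primary outcome (Section 9.1). This stands and limits the weight of the milk point.
- **Visit day need not be sample day, because milk may be collected at home.** This stands. It makes the count approximate and is a reason to record the collection date.

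**Conclusion.** The calendar inconsistency holds and needs no assumption about late visits. The day-33 statement and the counselling period do not fit women who start pack 1 on day 6 or 7, the lower end of Group 3's d-POP range does not follow from the pack, and the two start windows differ by 8 hours at the upper end (160 v 168). A reader might infer that some women will in fact lack contraceptive cover. The documents show only that the statement and the pack disagree.

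The milk-sample gap is a minor consequence. On-time samples are sound. About 0.1-1.3 Group 3 samples would be taken on d-POP, given the assumed 10-30% lateness, equal probability over days 29-35 and one reading of Section 7.3. A reader might go on to infer that Aim 2 is biased. The documents do not support that: nothing in them shows that a first to third d-POP capsule changes milk composition, and they give no late-visit rate. The effect on Aim 2 is probably small.

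**What to change.** 1. The sponsor must reconcile four items with the 28-capsule placebo pack: the start windows in Sections 6.1 and 8.1, Group 3's d-POP start range, the day-33 statement, and the counselling period. No value is proposed here.
2. State a milk-sample window that keeps the nominal 4-week time and ends at capsule 24 of pack 1, which is day 28, 29 or 30 for a start on day 5, 6 or 7. To include day 28 for every start day it must open no later than capsule 22. The rule is the same in all arms, so it does not unblind. Home collection, already allowed in Section 8.1, can help meet it if the visit slips.
3. Record the collection date and the capsule number on that day.
4. Keep all randomised women's samples in the main comparison and add a sensitivity analysis limited to in-window samples.

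The cost is revised wording, two recorded fields, one extra analysis and tighter booking. A woman who starts on day 5 has no margin after day 28. With 10 women per arm, the sensitivity analysis can only be descriptive.

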## 8 STUDY ASSESSMENTS AND PROCEDURES

### 8.1 EFFICACY ASSESSMENTS

This pilot study is a placebo-controlled double-blinded RCT. We will recruit women in the third trimester of pregnancy during their routine prenatal care clinical visits and post-partum (PP) during their hospital stay. Women will not be enrolled and randomized until after delivery. All women delivering at UCSD hospitals are offered comprehensive contraceptive counseling by nurse midwives or physicians during prenatal appointments and/or after delivery before discharge from the hospital.

#### **Enrollment Procedures:**

We will assess women who indicate that they desire POPs for contraception for eligibility after they have received contraceptive counseling. Research staff will identify postpartum women who are planning on utilizing POPs as postpartum contraception via review of medical records of patients receiving inpatient obstetrical services at UCSD. Study staff will visit these potential participants during their inpatient hospital stay to present the study and administer the pre-screening eligibility form if the patient is interested in participation. While only women who intend to use POPs for at least 8 weeks will be enrolled, all participants will be told if they are unhappy with POPs at any time, the study team will facilitate timely contraceptive counseling and referral to an appropriate provider to ensure that they can switch contraceptive methods at any time if they choose.

After enrollment and prior to randomization, participants will be asked to complete a brief self-administered demographic questionnaire using a private secure tablet that enters data directly into REDCap (Research Electronic Data Capture), a secure electronic data collection system. Demographic characteristics collected will include maternal age, race, Body Mass Index, gestational weight gain, parity, education, previous experience breastfeeding, previous contraceptive use history, breastfeeding intentions, delivery type and complications, infant stay in neonatal intensive care unit (and length of stay), infant birth weight, race, sex assigned at birth, and gestational age at birth. Participants will receive a gift card via text or email link for completing the survey.

[figure not shown]

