## 9.2 SAMPLE SIZE DETERMINATION

The sample size (N=30 in 6 months) was chosen to demonstrate feasibility to enroll 180 women in 36 months at our site during a larger multi-site trial and to successfully complete follow-up.

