## 9.4 STATISTICAL ANALYSES

### 9.4.1 GENERAL APPROACH

### 9.4.2 ANALYSIS OF THE PRIMARY EFFICACY ENDPOINT(S)

A survival analysis will be conducted to to assess time spent exclusively breastfeeding.

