### 9.4.3 ANALYSIS OF THE SECONDARY ENDPOINT(S)

Proportions will be compared using chi-square tests. ANOVAs will be used to calculate means for analysis using all 3 groups and t-tests for any pairwise comparisons.

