### 9.4.5 BASELINE DESCRIPTIVE STATISTICS

Baseline characteristics such as demographic information (age, education level, race, ethnicity and employment status) will be collected. At the time of enrollment, questions will also be asked about pregnancy history, past use of contraception, use of donor milk and current perception of adequacy of

human milk supply. Means and proportions of respondents in each of the two groups will be compared to assess for success of randomization.

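### Infant growth is compared by unadjusted tests on change scores, although ANCOVA on the same baseline value would probably be more precise at almost no cost

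*Combined protocol and SAP*

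**What the plan says.** All references are to the combined protocol and SAP.

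- **Endpoint.** The table in section 3 lists infant weight, length and head circumference as a change from baseline to 4 weeks. Aim 3 in the synopsis describes the same growth as starting at birth.
- **Baseline data.** Section 8.1 (Enrollment Procedures) collects, after enrolment and before randomisation, variables that include "parity, education, previous experience breastfeeding", and also infant birth weight, sex and gestational age. Birth length and head circumference are not on that list, although the change score needs a baseline value for each.
- **Analysis of means.** Section 9.4.3 uses ANOVA across the three groups and "t-tests for any pairwise comparisons". Section 9.1 sets the comparisons as group 1 against 2 and group 1 against 3, and names chi-square, Fisher exact and t-tests.
- **Use of baseline data.** Section 9.4.5 compares baseline characteristics between groups to see whether randomisation worked, and gives them no other use. The confounders mentioned under Surveys in section 8.1 are postpartum feeding practices and medications, to be explored without a stated model.
- **Size.** Section 6.1 gives 10 women per arm. Section 9.2 gives the reason: "The sample size (N=30 in 6 months) was chosen to demonstrate feasibility to enroll 180 women in 36 months".

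**The concern.** A change score subtracts the whole baseline value, so it sets the regression slope of the 4-week value on baseline to exactly 1. If the true slope is below 1, the change score over-corrects: infants who start heavier tend to show a smaller change whatever their arm. A t-test on the change then carries avoidable noise, and a chance difference between arms at birth passes partly into the estimated effect. ANCOVA estimates the slope from the data. The plan already needs a baseline value for each growth measure, so it gives up this precision without saving any data collection. At 10 per arm there is little precision to spare.

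**Working it through.** **The plan's own figure.** 3 arms × 10 = 30 women; 30/6 months = 5 per month; 5 × 36 = 180. Section 9.2 reproduces. It is a recruitment figure, and no power calculation is stated.

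**Inputs.** From the documents: 10 per arm, three arms, two pairwise contrasts, growth analysed as change. Assumed, because the documents do not give them: equal variances at baseline and 4 weeks, a correlation r of 0.5 to 0.7 (0.9 as a limit), and all 30 infants measured.

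**Variance ratio, large samples.** With common variance σ², the change score has variance 2σ²(1 − r), and the ANCOVA residual has variance σ²(1 − r²). The ratio is

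(1 − r²) / [2(1 − r)] = (1 + r)/2.

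**Cost of estimating the slope.** With one covariate the variance is multiplied on average by 1 + 1/(ν − 2), where ν is the within-group degrees of freedom.

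- Two-arm fit: ν = 18, factor 1 + 1/16 = 1.0625.
- Three-arm fit: ν = 27, factor 1 + 1/25 = 1.04.

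| r | (1 + r)/2 | × 1.0625 (two-arm) | × 1.04 (three-arm) |
|---|---|---|---|
| 0.5 | 0.75 | 0.80 | 0.78 |
| 0.7 | 0.85 | 0.90 | 0.88 |
| 0.9 | 0.95 | 1.01 | 0.99 |

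Over r = 0.5 to 0.7 the variance falls by about 10–20% (two-arm) or 12–22% (three-arm). Taking square roots, the standard error falls by about 5–11% or 6–12%.

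**Where the gain ends.** Two-arm: (1 + r)/2 = 16/17 gives r = 15/17 = 0.88. Three-arm: (1 + r)/2 = 25/26 gives r = 24/26 = 0.92.

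**Unequal variances.** The ANCOVA slope is r × (SD at 4 weeks / SD at baseline). The two methods differ only when this is not 1. A larger spread at 4 weeks moves a slope below 1 towards 1 and shrinks the gain. In the worst case (slope exactly 1), ANCOVA loses only the factor above: about 6% of variance two-arm, 4% three-arm.

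**Chance imbalance.** Two arms of 10 differ by at least 0.5 SD at baseline with probability 2[1 − Φ(0.5/√0.2)] = 0.26. Under equal variances, a 0.5 SD gap shifts the change-score difference by (1 − r) × 0.5 = 0.25 SD at r = 0.5 and 0.15 SD at r = 0.7. The standard error of that difference is √[2(1 − r) × 2/10] = 0.45 SD and 0.35 SD. The shift is therefore about 0.56 and 0.43 of a standard error.

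**Why one covariate.** With three covariates (birth weight, sex, gestational age) the factor is 1 + 3/14 = 1.214 two-arm and 1 + 3/23 = 1.130 three-arm. If the two extra variables predict nothing, the ratios become 0.91 and 1.03 two-arm, or 0.85 and 0.96 three-arm, at r = 0.5 and 0.7. Most or all of the gain is then spent.

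**The case against.** **The strongest case for leaving the plan alone.** This is a pilot sized for recruitment. A variance change of 10–20% alters no decision that the documents describe, the change score already uses the baseline value, and the correlation is unknown. All of this stands, and it limits the weight of the point. It does not favour the change score: the likely gain exceeds the small worst-case loss. Under randomisation both methods estimate the same arm difference, so Aim 3 is unchanged.

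**Stronger readings that the documents do not support.** A reader might infer any of the following.

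- *Every planned analysis, including the primary one, is unadjusted.* Section 9.4.2 says only "A survival analysis will be conducted to to assess time spent exclusively breastfeeding". It names no test, model or covariate, and section 9.4.1 has no text. That is a missing specification, not a stated unadjusted test.
- *Strong predictors are being ignored.* No section gives a correlation or prognostic effect for any baseline variable.
- *The trial could do with 15–25% fewer participants.* That reads (1 + r)/2 directly and omits the cost of estimating the slope.
- *Every continuous outcome has a usable baseline.* Milk composition is measured once, at 4 weeks. Section 9.4.5 asks at enrolment about "use of donor milk and current perception of adequacy of" the milk supply, but does not say that this is the lactation scale used as the outcome in section 3.
- *All baseline variables should be adjusted for.* Six covariates in a two-arm fit break even only at R² = 1 − 1/(1 + 6/11) = 0.35, or 0.23 in a three-arm fit.
- *The primary outcome should be stratified by previous breastfeeding.* Section 6.2 says "Participants will be randomized to their assigned group by chance with a computer-generated randomization scheme", which neither names nor excludes stratification. For a factor with 50% prevalence, arms of 10 differ by three or more women with probability 0.26. Yet with 60% exclusive breastfeeding (assumed), simulation gives a stratified risk difference 1.02 times the unadjusted variance for a 20-point prognostic effect and 0.89 times for 40 points. The gain may be nil.

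**Conclusion.** The point holds for infant growth. The plan specifies no covariate-adjusted analysis, defines growth as a change score and compares it by ANOVA and t-tests, although birth weight is collected before randomisation and the other two measures need a baseline value anyway. ANCOVA on that value would reduce variance by about 10–20% in a two-arm fit or 12–22% in a three-arm fit. This rests on equal variances, r of 0.5 to 0.7 and complete data. Near r = 0.9, or when the slope is close to 1, the gain is essentially gone. The unadjusted test remains valid, and chance imbalance is not bias. What is lost is some precision in a small pilot. The conclusion does not extend to the primary analysis or to milk composition.

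**What to change.** In section 9.4.3:

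1. Analyse 4-week infant weight by ANCOVA fitted to all three arms, with arm and birth weight as the only terms. Take the group 1 v 2 and group 1 v 3 contrasts, with confidence intervals, from that model.
2. Do the same for length and head circumference, each with the baseline measurement used in its change score. State what that baseline is, since the synopsis says birth and section 3 says baseline, and add the two measurements to the collection list in section 8.1.
3. Report the unadjusted change-score comparison as a sensitivity analysis.

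The cost is SAP wording and one residual degree of freedom (27 to 26 in the three-arm fit). No data are needed beyond those the change score already requires.

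Optional only: adjust the milk-supply scale for enrolment perception of supply if the two measures are comparable; stratify the randomisation or the primary analysis by previous breastfeeding.
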